2.4.4.3 Summary of results per time point

Central laboratory values (in conventional (US) and international units), percent change from baseline, and/or when appropriate absolute change from baseline (in conventional and international units), for HbA1c and FPG at Week 8, Week 12, Week 24, time points, will be summarized in the ITT population using:

• For HbA1c and FPG: LS mean and SE for each treatment group, obtained from the same MMRM models as used for endpoints above and including all planned time points and with raw values, changes from baseline, or percent change from baseline as response variable in the model as appropriate.

In addition, quantitative descriptive summaries by time point (value at visit and % change from baseline) will be presented for all variables using observed (ie, non-missing) data. In addition binary variables for HbA1c will also be described by time point.

And for other parameters bellow:

- Fasting SMPG,
- Change of mean 24-hour plasma glucose based on 8-point SMPG,
- Change in variability of fasting SMPG,
- Change in variability of 24-hour plasma glucose based on 8-point SMPG.

LS mean and SE for each treatment group, obtained from the same MMRM models as used for endpoints above and including all planned time points and with raw values, changes from baseline as response variable in the model as appropriate.

In addition, for all parameters quantitative descriptive summaries by time point (value at visit) will be presented for all variables using observed (ie, non-missing) data.

2.4.4.4 Multiplicity issues

To control the type I error, a hierarchical step-down testing procedure described by Hochberg and Tamhane will be applied for the primary efficacy endpoint to assess non-inferiority and superiority sequentially (see Section 2.4.4.1).

- Step 1: non-inferiority comparison of the mean change from baseline to Week 24 in HbA1c with Toujeo compared to Tresiba.
- Step 2: only if non-inferiority of Toujeo relative to Tresiba in step 1 is demonstrated, superiority of Toujeo over Tresiba in changes in HbA1c from baseline to Week 24 will be assessed.

No multiplicity adjustment will be made on secondary efficacy variables; 95% confidence intervals (95% CI) and P-values presented for these endpoints will be done for descriptive purpose only.

2.4.4.5 Additional efficacy analysis

Patient Reported outcomes

All PROs will be analyzed using the ITT population.

For each questionnaire a descriptive summary at each visit (baseline, Week 12 and Week 24) and change from baseline at Week 12 and Week 24 (except for DTSQc) will be provided, excluding data obtained after rescue therapy initiation, including:

- DTSQs total treatment satisfaction score (sum of items 1, 4, 5, 6, 7 and 8), "perceived frequency of hyperglycemia" (Item 2) and "perceived frequency of hypoglycemia" (Item 3) scores,,
- DTSQc total treatment satisfaction score (sum of items 1, 4, 5, 6, 7 and 8), "perceived frequency of hyperglycemia" (Item 2) and "perceived frequency of hypoglycemia" (Item 3) scores (atWeek 12 and Week 24 only)
- HABS confidence score (items 4, 6, 8, 11 and 14), anxiety score (items 2, 5, 7, 9 and 12) and avoidance score (items 1, 3, 10 and 13).

The change in DTSQs and HABS scores from baseline to endpoint are analyzed using an MMRM model similar as model used for quantitative secondary efficacy endpoints.

The change in DTSQs and HABS scores from baseline to endpoint are analyzed using a cumulative distribution functions of scores. Changes from baseline will be displayed by treatment groups, for each the 3 DTSQs/HABS scores and a graphical presentation will be used to illustrate trends over time per treatment arm by visit on mean scores $\pm \sqrt{2}$ SE and on change from baseline values $\pm \sqrt{2}$ SE.

Average scores at Week 12 and at Week 24 in total treatment satisfaction score, hyperglycemia perception and hypoglycemia perception score from DTSQc will be analyzed using an ANCOVA model. This model will include fixed categorical effects of treatment arm, on randomization strata of screening HbA1c (<8.0%, $\geq8.0\%$), randomization strata of SU or Meglitinides used at screening (yes/no), as well as continuous fixed covariates of corresponding baseline score from DTSQs.

Cumulative distribution function of week 24 scores will be plotted by treatment arm for each of the 3 DTSQc scores.

For interpretation of results, Effect Sizes (ES) using Cohen's definition will be calculated in order to interpret changes from baseline to Week 12 and Week 24 in PRO scores.

- Within ES: calculated at the treatment group level, when focusing on changes from baseline
- Between ES: Calculated when comparing treatment groups

The calculation of interpretation of ES are described on Section 2.5.1.

2.4.4.6 Analyses of exploratory efficacy endpoints

Subgroup analyses by baseline estimated GFR categories (mL/min/1.73m²): <60; ≥ 60 will be performed on the following endpoints:

- Percentage (%) of patients reaching target HbA1c <7% at Week 24 without severe and/or confirmed hypoglycemia (≤70 mg/dL) during the 24 weeks treatment period,
- Percentage (%) of patients reaching target HbA1c <7% at Week 24 without severe and/or confirmed hypoglycemia (<54 mg/dL) during the 24 weeks treatment period,
- Change of fasting SMPG from baseline to Week 24,
- Change in variability of fasting SMPG from baseline to Week 24.

2.4.5 Analyses of safety data

The summary of safety results will be presented by treatment group.

General common rules

All safety analyses will be performed on the safety population as defined in Section 2.3.2, unless otherwise specified, using the following common rules:

- Safety data in patients who do not belong to the safety population (eg, exposed but not randomized) will be listed separately,
- The baseline value is defined as the last available value prior to the first injection of IMP,
- The potentially clinically significant abnormality (PCSA) values are defined as abnormal vital signs values considered medically important by the Sponsor according to predefined criteria/thresholds based on literature review and defined by the Sponsor for clinical laboratory tests, vital signs, (PCSA version 3 dated May 2014 [Appendix A]),
- PCSA criteria will determine which patients had at least 1 PCSA during the treatmentemergent adverse event period, taking into account all evaluations performed during the treatment-emergent adverse event period, including nonscheduled or repeated evaluations.

The number of all such patients will be the numerator for the on-treatment PCSA percentage,

- The treatment-emergent PCSA denominator by group for a given parameter will be based on the number of patients assessed for that given parameter in the treatment-emergent adverse event period by treatment group on the safety population,
- For quantitative safety parameters based on reading measurements, descriptive statistics will be used to summarize results and change from baseline values by visit and treatment group. Summaries will include the last on-treatment value. The last on-treatment value is defines as the value collected at the same day/time of the last dose of investigational product. If this value is missing, this on-treatment value is the closest on prior to the last dose intake,
- The analysis of the safety variables will be essentially descriptive and no systematic testing is planned.

2.4.5.1 Analyses of hypoglycemia

All safety analyses of hypoglycemia events will be performed by treatment group in the safety population on events occurring during the TEAE period (as described in Section 2.1.4):

- Percentage (%) of patients with at least one hypoglycemia event will be presented for any hypoglycemia and for each hypoglycemia category of time: any time, nocturnal, daytime (as described in Section 2.1.4.1). The Odds Ratio and its corresponding 95% CI of Toujeo arm over Tresiba arm for each hypoglycemic event will be estimated by a logistic regression model using the same approach as the one described for categorical efficacy endpoint.
- Percentage (%) of patients with at least one hypoglycemia event will be presented for any hypoglycemia and for each hypoglycemia category of time: any time, nocturnal, daytime (as described in Section 2.1.4.1), excluding hypoglycemia occurring after the initiation of rescue therapy.
- Percentage (%) of patients with at least one hypoglycemia event, will be presented by study period (for ≤12 weeks, for >12 weeks to ≤24 weeks and during 24 weeks treatment period) for any hypoglycemia and for each hypoglycemia category (as described in Section 2.1.4.1). The Odds Ratio and its corresponding 95% CI of Toujeo arm over Tresiba arm for each hypoglycemic event will be estimated by a logistic regression model using the same approach as the one described for categorical efficacy endpoint.
- Percentage (%) of patients with at least one hypoglycemia event, will be presented by study period (for ≤12 weeks, for >12 weeks to ≤24 weeks and during 24 weeks treatment period) for any hypoglycemia and for each hypoglycemia category (as described in Section 2.1.4.1) excluding hypoglycemia occurring after the initiation of rescue therapy.
- Percentage (%) of patients with at least one severe hypoglycemia event will be summarized by symptom during 24 weeks treatment period),

- Number and rate of hypoglycemia event per patient-year will be summarized for any hypoglycemia and for each hypoglycemia category (as described in Section 2.1.4.1). For each hypoglycemic event ,the rate ratio, and its corresponding 95% CI, of Toujeo arm over Tresiba arm will be estimated using an over-dispersed Poisson regression model adjusted on randomization strata of screening HbA1c (<8.0%, ≥8.0%) and randomization strata of SU or meglitinides at screening (Yes vs No),
- Number and rate of hypoglycemia event per patient-year will be summarized for any hypoglycemia and each hypoglycemia category (as described in Section 2.1.4.1), excluding hypoglycemia occurring after the initiation of rescue therapy,
- Number and rate of hypoglycemia event per patient-year will be summarized by study period (for ≤12 weeks, for >12 weeks to ≤24 weeks and during 24 weeks treatment period) for any hypoglycemia and each hypoglycemia category (as described in Section 2.1.4.1), except probable and pseudo). Non classified hypoglycemia will be displayed. For each hypoglycemic event, the rate ratio, and its corresponding 95% CI, of Toujeo arm over Tresiba arm will be estimated using an over-dispersed Poisson regression model adjusted on randomization strata of screening HbA1c (<8.0%, ≥8.0%) and randomization strata of SU or meglitinides at screening (Yes versus No).

For Hypoglycemic ADA categories, in addition of threshold \leq 70 mg/dL (3.9 mmol/L), hypoglycemia episodes with plasma glucose <54 mg/dL (3.0 mmol/L) will be analyzed.

For each type of Hypoglycemia: Cumulative number and rate hypoglycemia event per 100 patientdays will be summarized by time of the day. Figures will be provided.

Cumulative mean number of hypoglycemia will be summarized over time using Nelson-Aalen estimates. Figures will be provided.

In addition, to help the interpretation of the results, an exploratory analysis defined as risk difference could be performed.

Subgroups analyses

The proportion of patients with at least one:

- Severe and/or confirmed (\leq 3.9 mmol/L [\leq 70 md/dL]) hypoglycemia,
- Severe and/or confirmed (<3.0 mmol/L [<54 md/dL]) hypoglycemia.

during the 24-week on-treatment period, will also be presented by the following subgroups:

- Age group (<65 and \geq 65 years of age),
- Gender (male, female),
- Baseline BMI (<30; [30 − 35[; ≥35 kg/m²),
- Randomization stratum of screening HbA1c ($\leq 8.0\%$, $\geq 8.0\%$),
- Randomization stratum of SU or meglitinides at screening (Yes vs No).

- Number of previous non-insulin anti-hyperglycemic agent (0, 1, 2, >2)
- Previous non-insulin anti-hyperglycemic treatment at screening, GLP-1RA (yes/no),
- Previous non-insulin anti-hyperglycemic treatment at screening: DPP-4 inhibitor (yes/no),
- Previous non-insulin anti-hyperglycemic treatment at screening: SGLT-2 inhibitor (yes/no),
- Duration of diabetes ($<10, \ge 10$ years),

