# 11.4.1.1 Extent of investigational medicinal product exposure

The duration of exposure during the study will be the total number of days of administration of IMP, ignoring temporary drug discontinuation.

The duration of exposure to the open-label IMP during the study is defined as:

(Date of the last IMP administration – date of the first IMP administration) + 1.

Duration of IMP exposure will be summarized descriptively as a quantitative variable (number, mean, SD, median, minimum, and maximum). In addition, duration of treatment exposure will

also be summarized categorically by numbers and percentages for each of the following categories and cumulatively according to these categories:

- up to 4 weeks
- >4 to 8 weeks
- >8 to 12 weeks
- >12 to 16 weeks
- >16 to 20 weeks
- >20 to 22 weeks
- >22 to 23 weeks
- >23 to 24 weeks
- >24 weeks

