If none of the above reasons can be found, and/or appropriate actions fail, it is recommended to initiate rescue therapy. The choice of the anti-diabetic treatment to be added to the basal insulin should be based on Investigator's decision and local labeling documents. Adding prandial insulin may be the preferred option. The addition of a new antidiabetic drug or increase in dose of background antidiabetic medication ("rescue") should not be decided based on a single FPG or HbA1c value but be based on a thorough evaluation of the patient's glycemic control.

Note: Short-term (up to 10 days maximum) uses of short/rapid-acting insulin therapy (eg, due to acute illness or surgery) will not be considered as rescue therapy.

All assessments for primary and secondary efficacy and safety parameters planned in final on treatment assessment visit (Visit 20) should be performed before adding the "rescue medication". Then the patient continues the IMP and stays in the study in order to collect safety information.

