2.1.4 Safety endpoints

The safety analysis will be based on:

- All hypoglycemia events (according to American Diabetes Association [ADA] Workgroup on Hypoglycemia),
- Local tolerability at injection site,
- Hypersensitivity reactions,
- Adverse events with special interest (AESI) with immediate notification:
 - Increase in alanine aminotransferases (ALT);
 - Pregnancy;
 - Symptomatic overdose with IMP/NIMP;
- Other adverse events (AE) or serious adverse events (SAEs),
- Vital signs including body weight.

In case of premature permanent IMP discontinuation or rescue therapy intake, the process described in Section 2.5.4 will be applied to retrieve safety assessments performed at the end of treatment visit or at pre-rescue visit.

Observation period for safety endpoints

The observation period of safety data will be divided into 3 segments:

• **The pre-treatment period** is defined as the time between the date of the signed informed consent and the first injection of open-label IMP.

- The on-treatment period (24-week on-treatment period / 24-week TEAE period) is defined as the time from the first injection of open-label IMP up to 7 days (or 2 days for hypoglycemia) after the last injection of open-label IMP, regardless of the introduction of rescue therapy. The 7-day interval is chosen based on the half-life of the IMP (approximately 5 times the half-life of Tresiba).
 - **12-week on-treatment period (12-week TEAE period)** is defined as the time from the first injection of IMP up to Week 12 or 7 days (or 2 days for hypoglycemia) after the last injection of IMP whichever comes earlier.
- **The post-treatment period** is defined as the time starting 8 days (or 3 days for hypoglycemia) after the last injection of open-label IMP (after on-treatment period). The baseline value for safety endpoints will be the last available value prior to the first injection of open-label IMP.

The on-study observation period is defined as the time from start of treatment until the end of the study (defined as last protocol planned visit or the resolution/stabilization of all serious adverse events and adverse events with pre-specified monitoring).

The baseline value for safety endpoints will be the last available value prior to the first injection of open-label IMP.

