2.4.3.2 Extent of investigational medicinal product exposure

The extent of IMP exposure will be assessed by the duration of IMP exposure.

Duration of IMP exposure is defined as last dose date – first dose date + 1 day, regardless of unplanned intermittent discontinuations (see Section 2.5.3 for calculation in case of missing or incomplete data). Duration of IMP exposure will be summarized descriptively as a quantitative variable (number, mean, SD, median, minimum, and maximum).

In addition, duration of treatment exposure will also be summarized categorically by numbers and percentages for each of the following categories and cumulatively according to these categories: up to 4 weeks, >4 to 8 weeks; >8 to 12 weeks; >12 to 16 weeks; >16 to 20 weeks; >20 to 22 weeks; >22 to 23 weeks; >23 to 24 weeks and > 24 weeks.

Additionally, the cumulative duration of treatment exposure will be provided, defined as the sum of the duration of treatment exposure for all patients, and will be expressed in patient years.

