2.5 DATA HANDLING CONVENTIONS

2.5.1 General conventions

The following formulas will be used for computation of parameters.

Reference day

The reference day for the calculation of extent of exposure, time to onset and relative days is the day of the first administration of IMP, denoted as Day 1.

Demographic formulas

Body Mass Index $(kg/m^2) = (Weight in kg)/(Height in meters)^2$.

Disease characteristics formulas

Duration of diabetes (years) = (Date of informed consent – date of diagnosis of diabetes +1)/365.25.

Age at onset of diabetes (years) = (Date of diagnosis of diabetes – date of birth +1) /365.25.

Duration of previous non-insulin anti-hyperglycemic treatment (years) = (Date of informed consent - date of first dose of previous non-insulin anti-hyperglycemic treatment +1) /365.25.

HbA1c transformation

To transform HbA1c in % to mmol/mol, the following formula is used:

IFCC = (10.93 * NGSP) - 23.50

NGSP (National Glycohemoglobin Standardization Program network) corresponds to HbA1c (%) and IFCC (International Federation of Clinical Chemistry network) to HbA1c (mmol/mol)

FPG and SMPG conversion From mg/dL to mmol/L: x 0.0555 From mmol/L to mg/dL: x 18.0148

Renal function formulas

No derivation because gender is not reported on e-CRF, so only central lab has this information.

Rate of hypoglycemia event per patient-year

Computed as [sum of number of episodes of hypoglycemia for all patients] / [sum of patient-year of exposure for all patients] with patient-year of exposure calculated per patient as number of days of exposure divided by 365.25.

Rate of hypoglycemia event per patient-year per study period:

- For ≤12 weeks: [sum of the number of episodes of hypoglycemia for all patients during the first 12 weeks] / [sum of patient-year of exposure for all patients during ≤12 weeks], with the patient-year of exposure during ≤12 weeks calculated as the number of days exposed during ≤12 weeks divided by (12x7),
- For >12 weeks to ≤24 weeks: [sum of the number of episodes of hypoglycemia since week 12 until week 24] / [sum of patient-year of exposure for all patients since week 12 until week 24], with the patient-year of exposure since week 12 until week 24 calculated as the number of days exposed since week 12 until week 24 (included) divided by (12x7),

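### The rescue-excluded hypoglycemia rate drops post-rescue events but, under the SAP's general exposure formula, keeps post-rescue time, so it is understated

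*SAP*

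**What the plan says.** SAP 2.4.5.1 lists several hypoglycemia rates. One is the number and rate per patient-year, for any hypoglycemia and for each category, "excluding hypoglycemia occurring after the initiation of rescue therapy". That bullet limits the events and says nothing about the time over which they are counted.

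The denominator comes from elsewhere:

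- SAP 2.5.1 defines the rate per patient-year as total episodes over total exposure, "with patient-year of exposure calculated per patient as number of days of exposure divided by 365.25".
- SAP 2.4.3.2 defines the duration of IMP exposure as "last dose date – first dose date + 1 day, regardless of unplanned intermittent discontinuations". Protocol 11.4.1.1 agrees: "The duration of exposure during the study will be the total number of days of administration of IMP, ignoring temporary drug discontinuation".
- The rescue therapy text in SAP 2.1.2 says what follows rescue: "Then the patient continues the IMP and stays in the study in order to collect safety information". Protocol 8.3.2 and 9 say the same.
- SAP 2.4.5.1 places its hypoglycemia analyses in the TEAE period of SAP 2.1.4, which ends 2 days (for hypoglycemia) "after the last injection of open-label IMP, regardless of the introduction of rescue therapy".

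A hypoglycemia period that does stop at rescue exists in SAP 2.1.3, but it is defined for efficacy endpoints, and 2.4.5.1 does not refer to it.

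**The concern.** The purpose of this summary is to show hypoglycemia without the influence of rescue treatment, which may include prandial insulin (SAP 2.1.2). That needs events and time from the same window. Read together, the sections above remove events at rescue but let exposure run on, so every post-rescue day counts as time in which no event could be recorded.

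Two things are at stake. First, the table will be read next to the main rate, which counts events regardless of rescue. Even if rescue changed nothing, the rescue-excluded rate would come out lower, and the gap could be taken for an effect of rescue on hypoglycemia. Second, if one arm accumulates more post-rescue time, its rate is pulled down further. With similar rescue timing in both arms, that is the arm needing more rescue, so poorer control would go with an apparently lower rate. Protocol section 4 singles out the hypoglycemia comparison as being of particular interest.

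**Working it through.** **Plan's own figure.** The documents state no expected hypoglycemia rate and no expected rescue rate, so there is no figure on this point to reproduce. The one design calculation, the HbA1c sample size, does reproduce (458 per arm against 460 stated; 90.1% power at 460), but it plays no part below.

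**Inputs from the documents.** Treatment lasts 24 weeks, or 168 days (SAP 1.4). The rescue thresholds apply from Week 12 (SAP 2.1.2; protocol 8.3.2). IMP continues after rescue. There are 460 patients per arm (SAP 1.3).

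**Assumptions.** The proportion rescued, f, the week of rescue, t, and the event rate are not in the documents. They are varied or stated below. Every patient is taken as exposed for the full 24 weeks.

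**Formula.** The planned rate and a matched rate share one numerator, the pre-rescue events. The constant that turns days into years cancels. So

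planned / matched = pre-rescue exposure / total exposure = 1 − f × (24 − t) / 24.

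**Shortfall of the planned rate.**

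| Rescued (f) | Rescue at Week 12 | Week 16 | Week 20 |
|---|---|---|---|
| 2% | 1.0% | 0.7% | 0.3% |
| 5% | 2.5% | 1.7% | 0.8% |
| 10% | 5.0% | 3.3% | 1.7% |
| 20% | 10.0% | 6.7% | 3.3% |

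The Week 12 column is the ceiling: f × 12/24 = f/2.

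With 6 post-rescue weeks on average:

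- 5% rescued: 0.05 × 6/24 = 1.25%
- 10% rescued: 0.10 × 6/24 = 2.5%
- 15% rescued: 0.15 × 6/24 = 3.75%

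**Worked case.** Take 460 patients, an assumed rate of 8.0 per patient-year both before and after rescue, and 10% rescued at Week 16.

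- Total exposure: 460 × 168 / 365.25 = 211.6 patient-years.
- Pre-rescue exposure: 211.6 × (1 − 0.10 × 8/24) = 204.5 patient-years.
- Pre-rescue events: 8.0 × 204.5 = 1636.
- Planned rate: 1636 / 211.6 = 7.73. Matched rate: 1636 / 204.5 = 8.00.

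The main rate would be 8.00, so the table would show a fall of 0.27 produced by the formula alone.

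**Two arms side by side, true rates equal.** The ratio of the planned rates is:

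- 10% against 5% rescued: 0.974 (rescue at Week 12) to 0.987 (Week 18).
- 15% against 5%, 6 post-rescue weeks in both: 0.9625 / 0.9875 = 0.975.
- 20% against 10%: 0.947 (Week 12) to 0.974 (Week 18).
- Equal rescue in number and timing: 1.000.

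**What drives the error.** It is post-rescue person-time, not the count of rescued patients. An arm with 10% rescued at Week 20 has a factor of 1 − 0.10 × 4/24 = 0.983. An arm with 5% rescued at Week 12 has 1 − 0.05 × 12/24 = 0.975. Here the arm with fewer rescues is understated more.

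**The case against.** The best reply is that this is an unstated detail. The bullet names no denominator, SAP 2.5.1 does not cite 2.4.3.2, and the first-to-last-dose definition sits in the section on extent of exposure. Elsewhere the documents match days to events: the by-period rates in SAP 2.5.1 use days exposed within each period, and the monthly rate in protocol 9.2.2 uses days exposed in its time window. SAP 2.1.3 even has a hypoglycemia period that stops at rescue. A programmer might therefore cut exposure at rescue unprompted.

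This shows that the authors could match time to events, not that they did so here. The by-period formulas cut at Week 12 and Week 24, the protocol's window is not defined by rescue, and SAP 2.1.3 concerns efficacy endpoints. The general formula and exposure definition are stated, and nothing exempts this summary from them.

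Three other parts of the reply do stand:

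- **No rate ratio is planned.** A reader might infer that the trial's modelled hypoglycemia comparison is biased. The documents do not support that. The over-dispersed Poisson model belongs to the main rate and the by-period rates; this bullet is only summarized, and SAP 2.4.5 calls the safety analysis essentially descriptive.
- **A higher rescue percentage need not mean a larger error.** A reader might infer that it always does. That holds only when rescue timing is similar in the two arms.
- **The size is assumed and probably modest.** Under SAP 2.1.2, rescue follows a check for other explanations and is not decided on a single value, which tends to shorten post-rescue time.

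**Conclusion.** The concern holds for one descriptive output. Applied as written, the SAP understates the rescue-excluded rate per patient-year by the share of exposure that is post-rescue. The direction is certain whenever any rescued patient continues IMP, and a larger sample does not reduce it.

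The ceiling is about half the proportion rescued. It rests on rescue starting no earlier than Week 12 and on full 24-week exposure; early discontinuation among patients not rescued would raise the share slightly. Under the assumed 5 to 15% rescued with 6 post-rescue weeks, the shortfall is 1.3 to 3.8%. Rates read side by side shift by about 1 to 3% for 10% against 5% rescued at the same time, and not at all if post-rescue time is balanced.

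The main rate is not affected, because it keeps post-rescue events and post-rescue time together. The percentage-of-patients analyses, with or without post-rescue events, have no person-time denominator. Nothing here bears on the primary HbA1c analysis.

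**What to change.** In SAP 2.4.5.1, with the formula in 2.5.1, state that for the rescue-excluded rate only, each patient's exposure runs from the first IMP dose to the earlier of the last IMP dose and the start of rescue therapy.

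The end point for patients not rescued should stay at the last IMP dose, as in the main rate. Ending it instead at the close of the hypoglycemia window, 2 days after the last dose, would put the two rates on different bases for most patients. Two days in 168 is 1.2%, about the size of the error at 5% rescued (1.25%).

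The cost is one sentence and one derived variable. The day rescue starts is already recorded in the e-CRF (protocol 8.3.2), so no new data are needed.
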